and $|M_E|$ is the margin of equivalence

and P_r is the probability of a rating

Clarification: Phase I will include up to 10 subjects and will be conducted before the firmware is going through formal validation. Phase II will include up to 30 subjects and will be conducted to validate the firmware.

Table 4 Endpoints, test methods and hypotheses

	Hypothesis	Test Method	Endpoint	Acceptance Criteria for phase I	Acceptance Criteria for phase II	Limitations, comments
A1	Sit to stand activity is perceived as better and not worse with the firmware update compared to previous.	Rating: worse, same, better (1-3)	Rating score 1-3	In average no more than 22.5% of the subjects should rate the firmware update no worse.	$H_0: P_{worse} = 0,333$ $H_1: P_{worse} < 0,333$ ∧ $H_0: P_{better} = 0,333$ $H_1: P_{better} > 0,333$ $\forall p < 0,05$	
A2	Stand to sit activity is perceived as better and not worse with the firmware update compared to previous.	Rating: worse, same, better (1-3)	Rating score 1-3	In average no more than 22.5% subjects should rate the firmware update no worse.	$H_0: P_{worse} = 0,333$ $H_1: P_{worse} < 0,333$ ∧ $H_0: P_{better} = 0,333$ $H_1: P_{better} > 0,333$ $\forall p < 0,05$	
B	Mobility is no worse with the firmware update compared to previous.	10mWT	Time in seconds	Exploratory	No significant increase in time needed to perform the 10mWT with the firmware upgrade. $H_0: \mu_0 - \mu_1 \geq M_{NI} $ $H_1: \mu_0 - \mu_1 < M_{NI} $ $M_{NI} = MDC$ $MDC = 0,13 \text{ m/s}^{13}$ $p < 0,05$	To be able to check if the knee keeps up with the user in a better way. Sensors logging
C	Mobility is no worse with the firmware update compared to previous.	2MWT	Distance in meters	Exploratory	No significant reduction in distance walked on 2MWT with the firmware upgrade. $H_0: \mu_0 - \mu_1 \geq M_{NI} $ $H_1: \mu_0 - \mu_1 < M_{NI} $ $M_{NI} = MDC$ $MDC = 34 \text{ m}^{14}$ $p < 0,05$	Sensors logging
D	Users perception of level-ground walking is no worse with the firmware update compared to previous.	Rating: worse, same, better (1-3)	Rating score 1-3	In average no more than 22.5% of the subjects should rate the firmware update no worse.	$H_0: P_{worse} = 0,333$ $H_1: P_{worse} < 0,333$ ∧ $H_0: P_{better} = 0,333$ $H_1: P_{better} > 0,333$	

					$\forall p < 0,05$	

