E	The PK firmware update shows no worse results in stair ascent activities compared to previous.	Stair assessment index	Rating score 1-13	Exploratory	$H_0: \mu_0 - \mu_1 \geq M_{NI} $ $H_1: \mu_1 - \mu_0 < M_{NI} $ $M_{NI} = 1$ point $p < 0,05$	Sensors logging ICCs of rs = 1.00 (p < 0.001) ¹²
F	Users perception of stair ascent is no worse with the firmware update compared to previous.	Rating: worse, same, better (1-3)	Rating score 1-3	Exploratory	$H_0: P_{worse} = 0,333$ $H_1: P_{worse} < 0,333$ \wedge $H_0: P_{better} = 0,333$ $H_1: P_{better} > 0,333$ $\forall p < 0,05$	
G	Users perception of exiting from stair ascent mode is no worse with the firmware update compared to previous.	Rating: worse, same, better (1-3)	Rating score 1-3	Exploratory	$H_0: P_{worse} = 0,333$ $H_1: P_{worse} < 0,333$ \wedge $H_0: P_{better} = 0,333$ $H_1: P_{better} > 0,333$ $\forall p < 0,05$	
H	Users perception of entering stair ascent mode is no worse with the firmware update compared to previous.	Rating: worse, same, better (1-3)	Rating score 1-3	Exploratory	$H_0: P_{worse} = 0,333$ $H_1: P_{worse} < 0,333$ \wedge $H_0: P_{better} = 0,333$ $H_1: P_{better} > 0,333$ $\forall p < 0,05$	

Secondary

I	Exiting stair ascent mode with the firmware update reduces unexpected movements compared to previous.	2 repetitions of Stair ascent	Count of unexpected movements	Exploratory	Significant reduction in unexpected movements when exiting stair ascent: $H_0: \mu_0 - \mu_1 \leq 0$ $H_1: \mu_0 - \mu_1 > 0$ $p < 0,05$	
J	Users perception with Power Knee and Pro-Flex Terra is no worse	Rating: worse, same,	Rating score 1-3	Firmware 2 will be tested: In average no more than 22.5%	Updated firmware will be tested : $H_0: P_{worse} = 0,333$	Sensors logging Activities :

	compared to the combination of the Power Knee and the prescribed foot.	better (1-3)		of the subjects should rate the combination no worse.	$H_1: P_{worse} < 0,333$ \wedge $H_0: P_{better} = 0,333$ $H_1: P_{better} > 0,333$ $\forall p < 0,05$	Walking on level ground (SSWS, slow and fast) Sit to stand and stand to sit Stair ascent and descent Ramp ascent and descent Squatting
--	--	--------------	--	---	--	--

Exploratory

K	Amount of time needed to perform 5XSST	5 times sit to stand test	Time in seconds			
L	Temporal spatial parameters during 5XSST	Moticon Insoles Xsens Optogait	Temporal spatial parameter s			
M	Temporal spatial parameters during 2MWT	Moticon Insoles Xsens Optogait	Temporal spatial parameter s			

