8.1 General

The test will be a randomized, controlled, double-blinded, cross-over investigation for both phases I and II.

Amputees are a small proportion of the general population. The population group specified in the inclusion/exclusion criteria is a further subsample of amputees. For practical reasons, i.e. to achieve statistical power, it is therefore more feasible to use within-subject comparison rather than creating study arms to compare. The results of the phase I data collection will be used subsequent to first testing, to further improve the tested device, i.e. PKM. Furthermore, as mobile amputees generally have and use a prosthetic device for their daily activities, within-comparison is feasible comparing to the subjects previous device.

All investigational activities will be conducted at prosthetic out-patient clinics.

As stated above the primary endpoint is the general usability of the Power Knee Firmware Update in ADLs, which are specifically explained in the secondary endpoints are (see **Table 4**) in that respective order of significance. See previous chapter on objectives and hypothesis and **Table 4** for rationale.

Drop-outs and withdrawals may be replaced if deemed necessary to fulfil the methodological standards of the study.

Instruments for data collection will include the following:

2MWT: 2-minute walk test

10mWT: 10-meter walk test

5XSST: 5 times sit-to-stand test

Specific questionnaire: In-house generated questionnaire on specific features in the investigation device.

Video

Data logging by Ossur Logic/ Ossur Toolbox

See chapter **10.2 Sample size calculation**.

Equipment required for each subject:

- Detailed protocol
- Chair with Armrests for 5XSST
- Measuring tape
- Markers and a measure corridor/course of known distance for 2MWT and 10mWT
- Video camera for video documentation
- PC to read out Ossur Logic and Ossur Toolbox results
- Case report forms (CRFs) – Tablet/computer OR printed out case report forms
- Investigational device: POWER KNEE with the Firmware Update
- POWER KNEE with the current marketed firmware
- Pro-Flex Terra feet
- Other components as applicable (pylons and adapters for fitting)
- Tools for fitting
- LASAR Posture equipment for alignment
- Xsens (Annex 17.5.1)
- Moticon Insoles (Annex 17.5.2)

- Optogait (Annex 17.5.3)
- Microgate Witty Timing Gate (Annex 17.5.4)

The equipment used does not require specific monitoring, or maintenance.

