10.1 Statistical design and procedures

Phase I

The dataset will be assessed with descriptive statistics only, comparing the means and variance for the two data points: prior-evaluation (current device with current firmware) and post-evaluation (investigational device with investigational firmware). Acceptance criteria for the data, as applicable, is defined in **Table 4 Endpoints, test methods and hypotheses**.

Phase II

The hypotheses (A1, A2, D, F, G, H, J) will be assessed with one sample binomial test. Other hypotheses will be tested using a two-tailed, paired, student's t-test (if the data are deemed to be normal) or using the Wilcoxon signed-rank test (if the data are deemed to be non-normal).

Subgroup analysis will not be performed as no subgroups are defined.

Repeated measures analysis has the advantage of increased power vis-à-vis group allocations and reduction in error variance associated with individual difference, as each subject acts as its own control. This is important for studying amputees as the group is a small proportion of the total population, and with specific inclusion/exclusion criteria the total eligible population becomes very small, making it difficult to find and recruit subjects to attain an acceptable level of power. This limited population pool often results in slightly heterogeneous sample, as the amputees available are few and far between, in every sense. Furthermore, no single amputation procedure and therefore amputated stump is exactly the same, making the experience of each amputee a bit unique. The within-subject design significantly reduces the individual differences when comparing the two conditions.

The drawback of the design is the potential of “carryover effects”, i.e. experience from one condition can affect outcome or performance in the other condition, creating a confounding extraneous variable that varies with the independent variable. Such effects are: practice, positive carryover effect to the latter condition; and fatigue, negative carryover effect to the latter condition

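### The only numerical Phase I acceptance criterion (Table 4, rows A1, A2, D and J) is inverted: it caps the share of subjects rating 'no worse' at 22.5%

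*Combined protocol and SAP*

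**What the plan says.** Section 7, Table 4 has a column of acceptance criteria for Phase I. Rows A1 (sit to stand) and D (level-ground walking) state: "In average no more than 22.5% of the subjects should rate the firmware update no worse". Row A2 (stand to sit) is the same but for two words: "In average no more than 22.5% subjects should rate the firmware update no worse". Row J, on the Power Knee combined with the Pro-Flex Terra foot, begins "Firmware 2 will be tested: In average no more than 22.5" per cent and ends "of the subjects should rate the combination no worse". Rows B, C and E to I are marked exploratory for Phase I, and K to N are blank, so 22.5% is the only numerical Phase I criterion.

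The ratings are worse, same or better. The hypotheses in A1 and A2 expect the update to be judged better rather than worse; those in D and J expect a judgement of no worse. For Phase II, the same four rows require the probability of a worse rating to be below 0.333 and that of a better rating to be above 0.333.

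On the role of Phase I:

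- Section 10.1: "The dataset will be assessed with descriptive statistics only", and "Acceptance criteria for the data, as applicable, is defined in" Table 4.
- Section 7, clarification: "Phase I will include up to 10 subjects and will be conducted before the firmware is going through formal validation".
- Section 8.1: "The results of the phase I data collection will be used subsequent to first testing, to further improve the tested device".
- Sections 2 and 7 allow Phase I to be repeated as often as needed.

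**The concern.** A cap on the share of subjects who find the update no worse rewards firmware that users dislike. Read literally, A1, A2 and D accept the update only when most raters call it worse, and J accepts the knee-and-foot combination on the same terms. J concerns a different object from the other three rows: it compares feet and, in Phase I, uses whichever firmware came second. The inversion is the same.

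Section 10.1 sends the Phase I data to this criterion, and Phase I precedes formal validation, so it is the implied standard for moving on. If it is followed, good firmware fails and poor firmware passes. If it is silently reversed, the report departs from the stated plan, and section 10.3 requires such departures to be approved by the sponsor and explained in the report.

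The averaging phrase at the start of each cell adds a second ambiguity. The sections available for this review do not say whether the average is over questionnaire items, activities or repetitions of Phase I.

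**Working it through.** **Direction.** Among subjects who give a rating, the share rating no worse equals 1 minus the share rating worse. A share of no worse at or below 22.5% is therefore a share of worse at or above 100% − 22.5% = 77.5%. The same holds for a mean over items or repetitions, so the direction is wrong whatever is averaged. Side by side for the same rows:

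| Source | Requirement on 'worse' |
|---|---|
| Hypotheses, A1, A2, D, J | update (or combination) not judged worse |
| Phase II criterion | below 0.333 |
| Phase I criterion as printed | at least 0.775 |
| Phase I criterion with 'no' deleted | at most 0.225 |

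**The plan's own figures.** The documents give no derivation for 22.5%, so there is nothing to reproduce for Phase I. The one computed result is the Phase II sample size in section 10.2: constant proportion 0.6666, effect size 0.2834003, N = 15, critical count 14. The alternative is 0.6666 + 0.2834003 = 0.9500003. With X the number of successes among 15:

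- Actual alpha = P(X ≥ 14 | 0.6666) = 0.0193871, as printed.
- Actual power = P(X ≥ 14 | 0.9500003) = 0.8290491, as printed.

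Reading 0.6666 as 1 − 0.333, the proportion not worse, Phase II counts 'not worse' as success and assumes about 95% of it, that is, about 5% worse. That direction is right, and it is opposite to the printed Phase I rule.

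**Size for Phase I.** Inputs: the 22.5% cap (Table 4) and n up to 10 (section 7). Assumptions: the rule is applied to one item, all n subjects rate it, and ratings are independent with true worse rates of 5% and 90%. The 90% rate is purely illustrative; 5% agrees with the reading of section 10.2 above.

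Let k = floor(0.225 × n). At n = 10, 0.225 × 10 = 2.25, so k = 2.

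- As printed: pass if the number rating no worse is at most k, that is, at least n − k rate worse (10 − 2 = 8 at n = 10).
- With 'no' deleted: pass if the number rating worse is at most k.

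At n = 10, as printed:

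- 5% worse: P(Bin(10, 0.95) ≤ 2) = 0.05^10 + 10(0.95)(0.05^9) + 45(0.95^2)(0.05^8) = 1.61e-9.
- 90% worse: P(Bin(10, 0.10) ≤ 2) = 0.9^10 + 10(0.1)(0.9^9) + 45(0.1^2)(0.9^8) = 0.930.

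Probability of passing, for n = 5 to 10:

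| n | k | Printed, 5% worse | Printed, 90% worse | 'No' deleted, 5% worse | 'No' deleted, 90% worse |
|---|---|---|---|---|---|
| 5 | 1 | 3.00e-5 | 0.919 | 0.977 | 4.6e-4 |
| 6 | 1 | 1.80e-6 | 0.886 | 0.967 | 5.5e-5 |
| 7 | 1 | 1.05e-7 | 0.850 | 0.956 | 6.4e-6 |
| 8 | 1 | 5.98e-9 | 0.813 | 0.943 | 7.3e-7 |
| 9 | 2 | 2.57e-8 | 0.947 | 0.992 | 3.0e-6 |
| 10 | 2 | 1.61e-9 | 0.930 | 0.988 | 3.7e-7 |

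**The case against.** The strongest reply is that little follows from the slip. Phase I is exploratory and descriptive, uses a convenience sample and may be repeated. No section makes progression to Phase II depend on this cell, and section 10.1 applies the criteria only where applicable. Any reader would see what was meant, and nobody would pass firmware because most users found it worse. On this view the pass probabilities describe an event that will not occur. This stands as a limit on the harm, but a stated threshold that must be reversed before use is still wrong as written.

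Three narrower points have merit.

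- **Denominator.** Subjects may skip blocks or decline tasks (section 8.4). If 2 of 10 skip, 1 rates worse and 7 rate no worse, then worse is 1/10 = 10%, within a 22.5% cap, but no worse is 7/10 = 70%, short of 77.5%. The two forms agree only among raters (1/8 = 12.5% and 7/8 = 87.5%).
- **Averaging.** The share 22.5% cannot be attained exactly on a single item for any n from 5 to 10, which fits an average over several items. The per-item counts above would then not be the criterion. The direction is unaffected. The questionnaire annexes (17.2 and 17.3) were not in the text available here and may define the averaging unit.
- **Intent.** Since 22.5% has no stated source, reading it as a cap on 'worse' is an inference, though the only one found that fits the rows. Even when corrected, it does not address the 'better' part of the hypotheses in A1 and A2.

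**Conclusion.** The concern holds. The Phase I criterion in A1, A2, D and J points the wrong way, against the hypotheses and the Phase II direction in the same rows, and nothing in the text reviewed reverses it. The wording recurs in four cells, so it is not a text-extraction fault. That conclusion needs no assumption beyond taking shares among subjects who give a rating.

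The probabilities rest on the per-item reading and the assumed worse rates. Over n = 5 to 10, the printed rule accepts 5%-worse firmware with probability at most 3.0e-5 and 90%-worse firmware with probability 0.81 to 0.95. With 'no' deleted, these become 0.94 to 0.99 and at most 0.0005.

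This should be corrected, but it does not threaten the trial's conclusions: no formal go/no-go rule depends on it, and the Phase II tests and sample size do not use it.

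**What to change.** In Table 4, Phase I column, delete 'no' before 'worse' in rows A1, A2 and D, and likewise in J for the combination. The criterion then caps the share rating worse at 22.5%, which among raters is the same as at least 77.5% rating no worse. When correcting the cells, the sponsor should:

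- confirm that 22.5% is the intended limit on 'worse' ratings;
- state that the denominator is the subjects who rated the item;
- add a clause saying what is averaged: items, activities or repetitions of Phase I.

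If the rule is applied per item, give the limit as a count, floor(0.225 × n): 1 'worse' rating for n = 5 to 8, and 2 for n = 9 or 10.

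The cost is one word in each of four cells and a short definition. Conduct, sample size and Phase II do not change.

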8.1 General

The test will be a randomized, controlled, double-blinded, cross-over investigation for both phases I and II.

Amputees are a small proportion of the general population. The population group specified in the inclusion/exclusion criteria is a further subsample of amputees. For practical reasons, i.e. to achieve statistical power, it is therefore more feasible to use within-subject comparison rather than creating study arms to compare. The results of the phase I data collection will be used subsequent to first testing, to further improve the tested device, i.e. PKM. Furthermore, as mobile amputees generally have and use a prosthetic device for their daily activities, within-comparison is feasible comparing to the subjects previous device.

All investigational activities will be conducted at prosthetic out-patient clinics.

As stated above the primary endpoint is the general usability of the Power Knee Firmware Update in ADLs, which are specifically explained in the secondary endpoints are (see **Table 4**) in that respective order of significance. See previous chapter on objectives and hypothesis and **Table 4** for rationale.

Drop-outs and withdrawals may be replaced if deemed necessary to fulfil the methodological standards of the study.

Instruments for data collection will include the following:

2MWT: 2-minute walk test

10mWT: 10-meter walk test

5XSST: 5 times sit-to-stand test

Specific questionnaire: In-house generated questionnaire on specific features in the investigation device.

Video

Data logging by Ossur Logic/ Ossur Toolbox

See chapter **10.2 Sample size calculation**.

Equipment required for each subject:

- Detailed protocol
- Chair with Armrests for 5XSST
- Measuring tape
- Markers and a measure corridor/course of known distance for 2MWT and 10mWT
- Video camera for video documentation
- PC to read out Ossur Logic and Ossur Toolbox results
- Case report forms (CRFs) – Tablet/computer OR printed out case report forms
- Investigational device: POWER KNEE with the Firmware Update
- POWER KNEE with the current marketed firmware
- Pro-Flex Terra feet
- Other components as applicable (pylons and adapters for fitting)
- Tools for fitting
- LASAR Posture equipment for alignment
- Xsens (Annex 17.5.1)
- Moticon Insoles (Annex 17.5.2)

- Optogait (Annex 17.5.3)
- Microgate Witty Timing Gate (Annex 17.5.4)

The equipment used does not require specific monitoring, or maintenance.

8.2 Investigational Device(s) and Comparator(s)

The subjects will be asked to use the investigational device with the updated firmware as they usually do with their primary prosthesis. The comparator device will be the Power Knee Mainstream with the latest firmware version released. It has the same intended use as the investigational device. Furthermore, they are indicated for the same condition and population group.

The subjects will be using the remaining part of their current prosthetic system with the investigational device, as it was used with the comparator device.

For Phase I, up to 10 subjects are to be enrolled, two per days and up to 3 investigational devices will be used.

For Phase II, up to 30 subjects are to be enrolled, two per days and up to 10 investigational devices will be used.

8.3 Subjects

All subjects will be dispositioned as follows:

Screen Failure: Subject did not pass screening procedures, not called in for clinical visit;

Candidate for enrollment: Passed screening procedures, accepts to come in for clinical visit;

Enrolled: Subject signs informed consent;

Fitted: Subject leaves the clinic on the investigational device;

Discontinued: Candidate for enrollment or Enrolled subject whose participation ended because they withdrew consent, were withdrawn by the Investigator, were lost to follow up, or died;

Table 5 Inclusion/Exclusion criteria

Inclusion:	Exclusion:
Only patients with the following characteristics are eligible for study entry:	Patients with the following characteristics are not eligible for study entry:
50Kg < body weight < 116Kg	Users with pain*
Lower limb loss, amputation or deficiency	Users with co-morbidities in the contralateral limb, which significantly affect their functional mobility (except bilateral amputees)
Cognitive ability to understand all instructions and questionnaires in the study	Users with cognitive impairments
Transfemoral amputees	Pregnant users***
MPK users who use Power Knee or who tried Power Knee within the last 3 years	
Bilateral amputees	
Hip disarticulation / Knee disarticulation amputees	
Age \geq 18 years	
Moderate to high-active users	
Willing and able to participate in the study and follow the protocol	
Comfortable and stable socket fit**	
No socket issues/changes in the last 6 weeks	

* Question on pain affecting their functional ability (yes/no)

** Socket fit: socket comfort score (SCS) over 7

*** Self-reported

A subject can withdraw from participation at any time, at his/her discretion, and this will not have any consequences for the participant's treatment. In such cases a report stating reasons for discontinuation of the participant shall be prepared by the LPI. No further investigational procedures concerning the subject will be conducted, except for a statement explaining the reason for withdrawal, including but not limited to: interacting or interviewing the subject in order to obtain data on him/her; obtaining additional private information on the subject by either observing the subject or collecting or receiving such information from any source.

The LPI can withdraw the participant from the trial at any time. The reasons shall be documented. There are no pre-specified criteria for discontinuation of participants from the trial. The discontinuation of participants in the trial

will not result in replacement with new participants. If withdrawal is due to problems related to the investigational device the participant will be asked for permission to follow the status/condition outside the clinical investigation. The follow-up will be individualized.

The LPI will initiate the recruitment process by screening potential participants from their customer database. This database includes individuals who have previously engaged with their services and fit the criteria for the study. In addition to the local database, participants may be recruited from Össur's customer database, external clinics and customers, word of mouth and/or customer representative meetings. The PI or LPI will establish communication with interested participants and will provide detailed information about the study.

For both phases, the visits to the clinic are expected to take 3-4 hours/subject. Total duration of phase I is therefore one week for every repetition and total duration of phase II is therefore up to three weeks.

The total time period required to implement the clinical investigation is expected to be up to 12 months. Each individual subject is expected to participate in the clinical investigation for the time mentioned above. The estimated time needed to include this number (enrolment period) is 1 month for phase I and 3 months for phase II.

At least 15 subjects are required to finish the protocol for statistical data analysis for phase II, see chapter **10.2 Sample size calculation**.

